14.5.3 Vital Signs

At each visit, summary statistics for the absolute vital sign value and the changes from baseline will be presented by treatment group. The significance of within-treatment changes from baseline will be assessed at the last visit, using the Wilcoxon Signed-Rank Test. The significance of between treatment changes from baseline will be assessed at the last visit using the Wilcoxon Rank-Sum.

14.5.4 Other Variables Related to Safety

No further variables related to safety will be analysed.

14.6 Interim Analyses

No interim analysis is planned for this study.

15 QUALITY CONTROL AND QUALITY ASSURANCE AUDIT

15.1 Monitoring

The study will be monitored by site visits and meetings with the Investigator and co-workers(s) at intervals agreed with the Investigator. The anticipated monitoring frequency will be stated in the Monitoring Plan. Monitoring will also involve, as appropriate, correspondence and telephone contacts.

The Investigator, or a designated member of the Investigator's staff, must be available at some time during the monitoring visit to review the data and resolve any queries and to allow direct access to the patient's records for source data verification.

At a site visit the CRFs forms should be made available in order that the accuracy of their completion may be checked. Each completed set of CRFs for each visit must be signed and dated by the Investigator, or a designated member of the Investigator's medical staff, to verify the data and statements submitted. Similarly all alterations must be initialled and dated by the Investigator or a designated person, explained as necessary, with the original mistake left legible.

15.2 Source Document Verification

On-site monitoring will also include source document verification (SDV). SDV is the procedure whereby the data contained in the CRFs are compared with the primary source data (e.g. patient notes, original recordings from automated instruments, X-ray films, ECG tracings, laboratory results) contained in the patient records held at the investigational site, and thereby verified as accurate.

The Investigator must be aware that:

- SDV is a part of the normal monitoring process. It will be carried out by designated study personnel and will be done in such a way as to preserve patient confidentiality, taking into account all ethical and legislative requirements.
- SDV will be carried out by direct comparison of entries made in the CRF with appropriate source data. Direct access to source data requires that the patient gives written, documented consent to this.
- Where source data are in the form of a computer print-out (e.g. medical records, ECG tracings) they will be made available by the Investigator to the monitor. Each will be signed and dated by the Investigator or a designated person, confirming that the print-out is a true and faithful record of the data for that patient. These print-outs will be filed in the CRF.
- The [REDACTED] Clinical Project Manager/Study Monitor will write an SDV Plan, specifying which data require SDV and what constitutes source data. This plan will also include the identification of any data to be recorded directly on the CRF and therefore considered source data. The SDV Plan will be agreed with the Investigator and documented in the Initiation Visit Report. For all patients, patient identity (date of birth, sex, initials and patient number), record of entry into the study and signature of informed consent must be verified from source documents as a minimum. In addition the following will be verified:
 - Endoscopy results
 - Details of SAEs.

It is important that the patient's notes record important details about their participation in the study. The Investigator or designated person will agree, as a minimum requirement, to record the following information in the patient's notes:

- Study number, brief description or title of study.
- Date that the patient gave written consent.
- All visit dates.
- All SAEs.
- All concomitant medications.

15.3 Audit

In accordance with the standards defined in ICH GCP, clinical studies sponsored by RB may be subject to an independent audit at the study site which will be conducted by personnel from an appropriate Quality Assurance Unit. Full consultation with the Investigator will be made prior to and during such audit, which will be conducted according to Quality Assurance Unit Standard Operating Procedures.

15.4 RB Policy on Fraud in Clinical Studies

In accordance with GCP, it is RB's policy always to follow up suspected cases of fraud.

16 ETHICS

16.1 Independent Ethics Committee/Institutional Review Board Review

Written approval of the study by an independent and appropriately constituted IEC/IRB must be obtained and a copy provided to RB before any protocol-related procedures that do not form part of the patient's normal clinical treatment are performed.

The approval letter must contain:

- Name and address of the IEC/IRB.
- Date of meeting.

- Sufficient information to identify the version of both the protocol and patient information/informed consent.
- Sufficient information to identify the version of other documents reviewed.

The investigator must also provide RB with a list of IEC/IRB members that includes each member's name, sex, and institutional affiliation.

The Investigator must submit all protocol amendments to the IEC/IRB for approval and notify them of any administrative changes.

16.2 Patient Information and Consent

Prior to entering the study, the Investigator or designated assistant will explain to each patient or legally acceptable representative, the nature of the study, its purpose, procedures, expected duration, alternative therapy available, and the benefits and risks involved in study participation. Patients will be given information and consent documents and the opportunity to ask questions. They will be informed of their right to withdraw from the study at any time without prejudice. After this explanation and before any study-specific procedures have been performed, the patient, or legally acceptable representative, will voluntarily sign and date the informed consent form. The person conducting the informed consent discussion and providing the information to the patient will also sign and date the consent form. Prior to participation in the study, the patient will receive copies of the written information and their signed and dated consent document, plus any other written information provided to them.

16.3 Informing General Practitioners

Not applicable.

17 REGULATORY REQUIREMENTS

17.1 Competent Authority Authorisation

This study proposal was submitted to the SFDA and approved on 4 June 2010. The approval number is 2010L02452.

17.2 Curriculum Vitae

A current curriculum vitae (CV) will be obtained from all personnel with significant study responsibilities, i.e. the Investigator and those to whom he or she has delegated some of his/her responsibilities as well as those whose names appear on the signature and delegation of duties forms (see below).

The CV will contain as a minimum the following information: name, current work address, qualifications, current position and previous positions. It will be signed and dated within 2 years of the start of the study. The CVs will be maintained on file by RB.

The Investigator and individuals to whom the Investigator has delegated some of his or her responsibilities as an investigator will be asked to provide sample signatures. The duties delegated to them will also be recorded on the signature and delegation of duties forms.

18 DATA HANDLING AND RECORD KEEPING

18.1 Case Report Forms (CRFs)

Electronic CRFs (eCRFs) will be used in this study. The Investigator is responsible for the quality of the data recorded in the eCRF. The data recorded should be a complete and accurate account of the patient's record collected during the study. The Investigator and study monitor will identify any data that will be recorded directly into the eCRF such that the eCRF will be considered the source document (i.e. no prior written or electronic record of the data). The study monitor will document this on the Initiation Visit Report.

The Investigator and other staff who have been delegated responsibility for entering data into the CRF at each visit will be trained in the use of the eCRFs before the first patient at that site is enrolled. The Investigator must review all entries for completeness and correctness. Data management will be conducted by Quintiles. The eCRF system will keep an audit trail of all changes made after the eCRF pages are initially completed and submitted.

The Investigator agrees to complete and sign the eCRFs in a timely fashion after completion of each patient and make them available to the study monitor for full inspection. In addition, any data queries prepared after the original eCRF has been completed should be answered promptly. Following monitoring of each patient's eCRF, the investigator will electronically sign the eCRF. Re-signature by the Investigator may be required prior to database lock after resolution of interim data queries.

Before acceptance, the study monitor will review the eCRFs for completeness and adherence to the protocol..Following completion of the study, the Investigator will no longer be able to access the eCRFs. They will therefore be provided with a CD with all of the eCRFs from their site by the data management group.

18.2 Retention of Essential Documentation

The Investigator should retain all essential documents (as defined in ICH E6 or according to other national and international regulations) until at least 5 years after the completion of the study. These documents should be retained for a longer period, however, if required by the applicable regulatory requirements or by an agreement with RB. It is the responsibility of RB to inform the Investigator when these documents no longer need to be retained.

Patient files and other source data must be kept for the maximum period of time permitted by the hospital, institution or private practice. The Investigator must notify RB if his/her institution's policy is to retain documents for a shorter period of time.

18.3 Protocol Amendments

The investigator must abide by the agreed protocol as approved by the IEC/IRB.

No change will be made to the agreed protocol without the prior written approval of the Investigator, the Clinical Project Manager, the R&D Manager Clinical (Healthcare) and the Global Medical Director, except in circumstances where the immediate safety of the patient is at risk. Written approval will also be obtained from other functions if appropriate, for example the Statistician if the amendment relates to a change in endpoints.

All substantial protocol amendments require IEC/IRB and regulatory approval. Protocol amendments will be submitted to the same IEC/IRB and regulatory authority as the study protocol.

19 CLINICAL TRIAL AGREEMENT

Before the study commences, a Clinical Trial Agreement will be signed in which financial aspects of the study (including financial disclosure) as well as responsibilities and obligations are described. This will take the form of:

- A contract between [REDACTED] and the Investigator/healthcare organisation.

20 COMPENSATION, INDEMNITY AND INSURANCE

20.1 Compensation

Appropriate treatment and/or compensation will only be provided and/or paid to the patient by the Sponsor to the extent that a patient suffers injury or death directly attributable to participation in the study without:

- Fault on the part of the investigator or the CRO or its employees or agents.
- The investigator or the CRO failing to comply with the protocol.
- The investigator or the CRO failing to notify the Sponsor of the claim or denying the Sponsor full conduct of the claim.

In any event, such compensation and treatment shall only be provided by the Sponsor to the extent required by the applicable law.

20.2 Indemnity

RB will provide appropriate indemnity for the Investigator and staff who conduct part or all of this study, upon request. The request must be received before the first patient is recruited.

20.3 Insurance

If required, and in accordance with applicable regulatory and legal requirements, RB will take out appropriate insurance policies on behalf of the Investigator and staff who conduct part or all of this study, and/or on behalf of the patients participating in the study.

21 REPORTING, PUBLICATION AND PRESENTATION

A clinical study report will be prepared according to ICH E3 (Structure and Content of Clinical Study Reports) as part of RB's commitment to Good Clinical Practice. The report will be a record of the total study conduct and findings, and will be subject to approval by the Co-ordinating Investigator who will sign the final report.

The study data will be owned by RB. RB retains the right to publish the data independently of the Investigator. RB agrees that before it publishes the results, it will provide the Investigator with at least 30 days for full review prior to submission of the manuscript to the publisher. The Investigator must submit any proposed manuscript to RB for approval prior to submission for publication.

Any publication must state that it is a part of a multicentre study. Where it would be impractical to send the manuscript to every Investigator in a multicentre study, a copy will be sent to the Co-ordinating Investigator. In such a study, RB may wish to publish the results of the study and this may be done without all participants having the opportunity to review the manuscript.

23 APPENDICES

23.1 Appendix 1 English version Reflux Disease Questionnaire

Reflux Disease Questionnaire (RDQ)						
Please answer each question by ticking one box per row.						
1. Thinking about your symptoms over the past 7 days, how often did you have the following?						
	Did not have	1 day	2 days	3-4 days	5-6 days	Daily
a.						
b.						
c.						
d.						
e.						
f.						
2. Thinking about your symptoms over the past 7 days, how would you rate the following?						
	Did not have	Very mild	Mild	Moderate	Moderately severe	Severe
a.						
b.						
c.						
d.						
e.						
f.						

23.2 Appendix 2 Chinese Mandarin version Reflux Disease Questionnaire

Version B

反流性疾病问卷调查(RDQ)

回答每条问题时, 请在每行其中一个空格内加上「✓」号。

1. 回想过去 7 天, 你出现以下症状有多频繁?

	无	1星期 少于 1 天	1星期 1 天	1星期 2-3 天	1星期 4-6 天	每天
a. 胸骨后感到灼热						
b. 胸骨后感到疼痛						
c. 上腹中心感到灼热						
d. 上腹中心感到疼痛						
e. 口腔内有酸味						
f. 有东西从胃部向上 移动而感到不适						

2. 回想过去 7 天, 你认为以下症状出现时的程度如何?

	无	很轻微	轻微	中度	较严重	严重
a. 胸骨后感到灼热						
b. 胸骨后感到疼痛						
c. 上腹中心感到灼热						
d. 上腹中心感到疼痛						
e. 口腔内有酸味						
f. 有东西从胃部向上 移动而感到不适	

1. LIST OF ABBREVIATIONS

Abbreviation	Definition
AE	Adverse event
ANOVA	Analysis of Variance
BLQ	Below the lower limit of quantification
CI	Confidence Interval
CRF	Case report form
CSP	Clinical Study Protocol
FAS	Full analysis set
GERD	Gastro-esophageal reflux disease
IMP	Investigational medicinal product
ITT	Intention-to-Treat
MedDRA	Medical Dictionary for Regulatory Activities
NIMP	Non-investigational medicinal product
OTE	Overall treatment evaluation
PP	Per protocol
PT	Preferred term
RDQ	Reflux Disease Questionnaire
SAE	Serious adverse event
SOC	System organ class
SAP	Statistical analysis plan
SI	International System
ULQ	Upper limit of quantification
WHO	World Health Organization

2. INTRODUCTION

This document describes the rules and conventions to be used in the presentation and analysis of efficacy and safety data for Protocol GA1210. It describes the data to be summarized and analyzed, including specifics of the statistical analyses to be performed.

This statistical analysis plan (SAP) is based on clinical study protocol (CSP) version Final v 2.0 Amendment 1, dated 04Jun2013.

Document: Reckitt Benckiser GA1210 Statistical Analysis Plan

Author: [REDACTED]

Version Number:

2.0

Version Date:

29Jul2014

Template No: CS_TP_BS016 – Revision 3

Reference: CS_WI_BS005

Effective Date: 01May2012

Page 7 of 23

3. STUDY OBJECTIVES

3.1. PRIMARY OBJECTIVE

The primary objective is to assess the efficacy of Compound Sodium Alginate Double Action Chewable Tablets compared with a matched placebo in reduction of the symptoms of Gastro-esophageal reflux disease (GERD) in patients with GERD as assessed using the Reflux Disease Questionnaire (RDQ).

3.2. SECONDARY OBJECTIVES

The secondary objectives of this study are to assess the efficacy of Compound Sodium Alginate Double Action Chewable Tablets compared with matching placebo in reduction of the symptoms of heartburn, acid regurgitation and dyspepsia in patients with GERD.

Other secondary objectives include the efficacy of Compound Sodium Alginate Double Action Chewable Tablets compared with placebo in patient responsiveness / satisfaction and comparison of safety in terms of adverse events.

3.3. SAFETY OBJECTIVES

Safety will be assessed in terms of the overall proportion of patients with adverse events (AEs).

4. STUDY DESIGN

4.1. GENERAL DESCRIPTION

This is a multi-centre, randomised, double blind, two-arm, placebo-controlled, parallel group study. After signing a written informed consent, patients will undergo a screening period of up to 7 days. Patients who satisfy the study entry requirements within 7 days of consent, will be randomised to receive either Compound Sodium Alginate Double Action Chewable Tablets (2 tablets four times daily) or matching placebo tablets (2 tablets four times daily), for a 7-day treatment period. At the beginning and end of the treatment period, patients will be required to complete the RDQ.

In addition, at the end of the 7-day treatment period, patients will be required to complete the overall treatment evaluation (OTE).

The sample size calculation, based on the UK pilot study and a previous pivotal China study, shows that 1054

Document: Reckitt Benckiser GA1210 Statistical Analysis Plan

Author: [REDACTED]

Version Number:

2.0

Version Date:

29Jul2014

Template No: CS_TP_BS016 – Revision 3

Reference: CS_WI_BS005

Effective Date: 01May2012

Page 8 of 23

evaluable patients need to complete the study (with the aim of having approximately 527 patients in each treatment group). An evaluable patient is defined as a randomised patient who completes the study treatment period and attends the end of treatment visit. In order to achieve this, it is estimated that approximately 1222 patients will have to be screened and approximately 1100 patients will have to be randomized.

Patients can enter the study, if eligible, following informed consent at Visit 1. A maximum of 7 days will be allowed to screen a patient at Visit 1. If eligible, the patient will be randomised and will commence the 7-day treatment period at Visit 2 (Day 0) to receive either Compound Sodium Alginate Double Action Chewable Tablets or matching placebo tablets. Visit 3, the End of study visit, will occur on Day 8 (between Day 7 and Day 10).

4.2. SCHEDULE OF EVENTS

Schedule of assessments can be found in Section 3.10 of the protocol.

5. FINAL ANALYSIS

All final, planned analyses identified in this SAP will be performed by Quintiles Biostatistics following Reckitt Benckiser's Authorization of this SAP, Database Lock and Sponsor Authorization of Analysis Sets.

6. ANALYSIS SETS

Agreement and authorization of patients included/excluded from each analysis set was conducted at a blind data review meeting on 23rd July 2014, prior to database lock.

6.1. ALL PATIENT [AP] POPULATION

All patients recruited (e.g. those with eligibility confirmed at screening visit and assigned randomization number) into the study will be included in the All Patient Population.

6.2. SAFETY POPULATION [SAF]

All patients who are recruited into the study and receive at least one dose of study medication will be included in safety population.

Document: Reckitt Benckiser GA1210 Statistical Analysis Plan

Author: [REDACTED]

Version Number:

2.0

Version Date:

29Jul2014

Template No: CS_TP_BS016 – Revision 3

Reference: CS_WI_BS005

Effective Date: 01May2012

Page 9 of 23

6.3. INTENT-TO-TREAT [ITT] POPULATION

All patients who are recruited into the study and have at least partially completed RDQ questionnaire for the trial therapy period or are known to have withdrawn from the study due to poor efficacy will be included into intent-to-treat (ITT) population.

6.4. PER PROTOCOL [PP] POPULATION

The inclusion/exclusion from per protocol (PP) population was confirmed during a blind data review meeting on 23rd July 2014, and will include all patients from the ITT population who have no major protocol deviations or other circumstances that may be relevant to efficacy assessment during the study.

A major protocol deviation that affects efficacy assessment is defined as any deviation of the protocol that is considered to affect the efficacy results and will include the following:

- Patient did not satisfy an inclusive/exclusive criteria that was deemed to have potential to affect efficacy;
- Patient took prohibited medication which would interfere with evaluation of drugs in the study period;
- Patient had inadequate treatment compliance. Adequate compliance with the treatment is defined as $\geq 75\%$ of study medication used from return tablet count.

Additionally, a patient will be excluded from the PP population if they returned for Visit 3/Early termination visit outside the 7 – 10 day window and did not withdraw for lack of efficacy

7. GENERAL CONSIDERATIONS

7.1. REFERENCE START DATE AND STUDY DAY

Study Day will be calculated from the reference start date, and will be used to show start/stop day of assessments and events.

Reference start date (Day 0) is defined as the day of randomisation.

- Study Day = (date of event – reference start date).

In the situation where the event date is partial or missing, Study Day, and any corresponding durations will appear partial or missing in the listings.

Randomization date will be considered as the same date of randomization visit, that is, visit 2.

7.2. BASELINE

Unless otherwise specified, baseline value refers to the tests or measurements recorded at Visit 1, screening

Document:	Reckitt Benckiser GA1210 Statistical Analysis Plan		
Author:	[REDACTED]	Version Number:	2.0

Template No: CS_TP_BS016 – Revision 3

Reference: CS_WI_BS005

Effective Date: 01May2012

Version Date:

29Jul2014

Page 10 of 23

visit. If a particular test or measurement was repeated after Visit 1, screening visit, then the baseline value is defined as the last non-missing measurement taken prior to Visit 2, Day 0 (including unscheduled assessments). Baseline for RDQ scores are collected on Day 0. In the case where the last non-missing measurement and the reference start date coincide, that measurement will be considered pre-baseline, but Adverse Events (AEs) and medications commencing on the reference start date will be considered post-baseline.

7.3. RETESTS, UNSCHEDULED VISITS AND EARLY TERMINATION DATA

In general, for by-visit summaries, data recorded at the nominal visit will be presented. Unscheduled measurements will not be included in by-visit summaries. In the case of a retest (same visit number assigned), the latest available measurement for that visit will be used for by-visit summaries.

Early termination data will be mapped to the next available visit number, i.e., Visit 3, for by-visit summaries.

Listings will include scheduled, unscheduled, retest and early discontinuation data.

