11.6 Unscheduled Visits

If unscheduled visits occur, the Investigator must record the following in the patient's CRF:

- Reason for unscheduled visit
- Any AEs.
- Concomitant medication and therapy changes.
- Withdrawal (if deemed appropriate).
- Any clinical assessments deemed appropriate for the clinical care of the patient.

If the dosage regimen of study medication has been changed, the Investigator must contact the RB Clinical Project Manager in order to determine if the patient should be withdrawn from the study or may be allowed to continue. The Clinical Project Manager will advise the Investigator of how information should be recorded on the CRF.

Unscheduled visits should not alter the timing of the routine study schedule.

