16.3 LABORATORY EVALUATIONS

Clinical assessments on hematology and clinical chemistry are to be measured at Visit 1 and Visit 3 or Early Termination Visit. A list of laboratory assessments to be included in the outputs is provided in appendix 1. Local laboratories will be used for the assessment of hematology and clinical chemistry data and these data will be converted to the International System (SI) of units by Data Management Team using standard conversion factors. Quantitative laboratory measurements reported as "< X", i.e. below the lower limit of quantification (BLQ), or "> X", i.e. above the upper limit of quantification (ULQ), will be converted to X for the purpose of quantitative summaries, but will be presented as recorded, i.e. as "< X" or "> X" in the listings.

At each visit, summary statistics for the absolute laboratory value and the changes from baseline will be presented by treatment group. The significance of within-treatment changes from baseline will be assessed using the Wilcoxon Signed-Rank Test. The significance of between treatment changes from baseline will be assessed using the Wilcoxon Rank-Sum Test. Statistical testing will be performed at last visit.

Each pre-study baseline laboratory value will be categorised as low, normal, or high based on the reference range of the local laboratories:

- Low: Below the lower limit of the laboratory reference range.
- Normal: Within the laboratory reference range (upper and lower limit included).
- High: Above the upper limit of the laboratory reference range.

Each post-baseline value will be classified in a similar manner, producing a 3 x 3 table for each treatment group at each post-baseline visit. Scores of "1" will be assigned to low values, "2" to normal values, and "3" to high values. Using these scores, shifts from baseline will also be assigned a score. For example, a laboratory value that shifts from low to high will be assigned a score of 2, whilst a laboratory value that remains at a low value will be assigned a score of 0. Shifts between these categories between baseline and subsequent timepoints (Visit 3

Document: Reckitt Benckiser GA1210 Statistical Analysis Plan

Author:

Version Number:

2.0

Version Date:

29Jul2014

Template No: CS_TP_BS016 – Revision 3

Effective Date: 01May2012

Reference: CS_WI_BS005

Page 20 of 23

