or Early Termination Visit) will be compared using the Wilcoxon Signed-Rank test within each treatment group. Statistical testing will be performed at last visit.

In addition to the high and low quantitative laboratory assignments (as identified by means of the laboratory reference ranges), clinically significant quantitative laboratory assessments will be identified by investigator and the result will be recorded in the eCRF. The number and percentage of patients with abnormal or clinically significant results will be tabulated by treatment groups by visit. The results will also be listed.

Women of child-bearing potential will undergo urine pregnancy testing (positive or negative). The results will be listed.

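### An abnormal Visit 3 laboratory value that normalises on a same-visit retest, or an abnormal value seen only at an unscheduled visit, can be missing from the SAP's laboratory tables

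*SAP*

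**What the plan says.** SAP 7.3 sets two selection rules for by-visit summaries. For repeats: "In the case of a retest (same visit number assigned), the latest available measurement for that visit will be used for by-visit summaries". For extra visits: "Unscheduled measurements will not be included in by-visit summaries". It maps early termination data to Visit 3 and adds: "Listings will include scheduled, unscheduled, retest and early discontinuation data".

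SAP 16.3 gives the sampling times: "Clinical assessments on hematology and clinical chemistry are to be measured at Visit 1 and Visit 3 or Early Termination Visit". Its laboratory outputs are built by visit:

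- Summaries: "At each visit, summary statistics for the absolute laboratory value and the changes from baseline will be presented by treatment group".
- Shifts: classification as low, normal or high, "producing a 3 x 3 table for each treatment group at each post-baseline visit".
- Abnormality counts: "The number and percentage of patients with abnormal or clinically significant results will be tabulated by treatment groups by visit".

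The Wilcoxon tests are run at the last visit, which Protocol 14.5.2 defines as Visit 3 or the Early Termination Visit. SAP 7.5 defines change as the value at a visit minus baseline.

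The baseline rule in SAP 7.2 differs: the last non-missing value before Day 0 is used, and unscheduled assessments count. Protocol 11.6 foresees that an unscheduled visit may include the following: "Any clinical assessments deemed appropriate for the clinical care of the patient".

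**The concern.** Each patient has one scheduled post-baseline laboratory sample. If its result is abnormal and a repeat under the same visit number is normal, the repeat takes its place and the patient appears as normal. A result that the investigator marked as clinically significant could then leave the table meant to count such results. No first-value, worst-value or any-post-baseline table would bring it back.

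The latest-value rule has no direction in itself. The direction comes from why samples are repeated. Where a repeat is prompted by an abnormal result, the rule can only keep or remove that abnormality, so the tables move towards normal in both arms.

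A second, separate gap concerns unscheduled visits. A patient whose only abnormal post-baseline value comes from such a visit is not tabulated at all, although an unscheduled value before Day 0 may serve as baseline.

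At stake is how completely the laboratory tables describe abnormalities. These include sodium and calcium, which are measured (Protocol 13.4) and which the Protocol introduction links to named risks. Efficacy is not affected.

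**Working it through.** The documents state no figure on this point, so there is none to reproduce. The check has two parts.

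**1. Follow one patient's values through SAP 7.3 and 16.3**

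| Course after baseline | Value tabulated | Abnormality counted? |
|---|---|---|
| Visit 3/ET abnormal, no repeat | Visit 3/ET | Yes |
| Visit 3/ET abnormal, same-visit repeat still abnormal | Repeat | Yes |
| Visit 3/ET abnormal, same-visit repeat normal | Repeat | **No** |
| Visit 3/ET abnormal, recheck logged as unscheduled | Visit 3/ET | Yes |
| Visit 3/ET normal, abnormal only at an unscheduled visit | Visit 3/ET | **No** |

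The loss arises in the third and fifth rows only. In the fourth row the unscheduled rule keeps the abnormal value in the tables.

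Whether the last-visit tests inherit the rule is an inference. SAP 7.3 opens with a general qualifier and speaks of summaries, not tests. But the tests use values or changes at Visit 3/ET, SAP 7.5 computes change from the value at a visit, and 7.3 is the only rule that says which of several values at a visit is used.

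**2. How large the third row could be**

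Let q be the share of first-sample abnormalities repeated under the same visit number, and r the share of those repeats that are normal. Then:

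share still counted = 1 − q × r

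Both q and r are assumptions. For illustration, also assume true abnormality rates of 4% and 2%, with 1100 / 2 = 550 patients per arm (the 1100 is from Protocol 14.1). True expected counts are 550 × 0.04 = 22 and 550 × 0.02 = 11.

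| q | r | Share counted | Expected counts | Difference (points) | Approximate power |
|---|---|---|---|---|---|
| 0 | any | 1 − 0 = 100% | 22.0 vs 11.0 | 2.00 | 49% |
| 0.25 | 0.3 | 1 − 0.075 = 92.5% | 20.4 vs 10.2 | 1.85 | 46% |
| 0.5 | 0.5 | 1 − 0.25 = 75% | 16.5 vs 8.25 | 1.50 | 39% |
| 0.9 | 0.8 | 1 − 0.72 = 28% | 6.2 vs 3.1 | 0.56 | 17% |

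The difference is (4% − 2%) × share counted. Power is for a two-sided 5% comparison of two proportions. The SAP plans no such test on these counts, so the power column only shows how far the information would thin out.

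With the same q and r in both arms, the 2:1 ratio is unchanged in every row; the absolute difference and the counts shrink. The fifth row of the first table cannot be sized, because the documents give no rate of unscheduled sampling.

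**The case against.** The strongest case against is that this is a narrow, conditional gap in secondary tables. The documents describe no Visit 3 retest procedure and give no retest rate. Repeats may be made for failed samples, and a later recheck may be follow-up of an adverse event rather than a retest with the same visit number. The stated safety measure is the proportion of patients with adverse events. Protocol 13.4.4 requires the investigator to comment on all abnormal values and identify the clinically significant ones, and Protocol 13.1.4 lets a significant laboratory abnormality be an adverse event, which brings it into the adverse event tables and Fisher's tests. Patients who stop early have laboratory tests at the Early Termination Visit, and these are mapped to Visit 3.

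Most of this stands, and it limits the point. It does not remove it. The adverse event route takes only abnormalities judged significant, so other out-of-range values reach a comparison by arm only through the laboratory tables. Listings keep the values but do not compare arms.

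Four stronger readings are tempting and are not supported:

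- **That the unscheduled rule also removes abnormal Visit 3 values.** It does not; the Visit 3 value stays.
- **That an on-drug value is replaced by an off-drug one.** Dosing starts the day after Day 0 and lasts seven days, and Visit 3 is preferably on Day 8, so the scheduled sample is normally already after the last dose.
- **That the safety conclusion is wrong.** The adverse event analyses and the listings do not depend on this rule.
- **That a sodium or calcium signal is being hidden.** Nothing shows this. The Protocol excludes known hypercalcaemia and patients who need a low-sodium diet, and it studies the minimum dose.

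**Conclusion.** The point holds in a limited form. The text of SAP 7.3 and 16.3 is clear: an abnormal Visit 3/ET laboratory value that normalises on a same-visit retest can drop out of the by-visit summaries, the shift table and the abnormality counts. An abnormal value seen only at an unscheduled post-baseline visit is not tabulated. That the last-visit tests follow the same rule is a reasonable inference from SAP 7.5, not a written statement.

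The size is unknown. The retest effect is zero with no same-visit retests. Under the assumed non-zero rates above, 92.5% down to 28% of first-sample abnormalities would still be counted. The expected direction, towards normal in both arms, rests on the assumption that repeats are prompted mainly by abnormal results. Equal retesting and normalisation in the two arms would leave the risk ratio intact. This is an inexpensive improvement to the laboratory tables, not a threat to the trial's conclusions.

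**What to change.** In SAP 7.3 and 16.3, state that the post-baseline counts of abnormal and clinically significant laboratory results, and the low/normal/high shift, are based on the worst post-baseline value. Include first samples, retests and unscheduled values, and leave out only samples documented as technically invalid. Say how a patient with both a low and a high post-baseline value is handled, since the shift table is two-sided. Keep the last pre-dose value as baseline, as SAP 7.2 has it.

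Replacing the latest value by the first valid one in every summary and test, or extending the change to vital signs, is more debatable and is not needed to close this gap.

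The cost is SAP wording and a little extra programming; no new data are needed. The drawback is that reported abnormality rates may rise slightly in both arms, because the worst of several post-baseline values is set against a single baseline value. A footnote to the tables should say so.
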